RBC	Red blood cell
RCD-II	Type II Refractory Celiac Disease
RE	Role limitations due to emotional problems
SAE	Serious adverse event
SAP	Statistical analysis plan
SC	Subcutaneous
sCD3-	Surface CD3-negative
sCD8-	Surface CD8-negative
SD	Standard deviation
SOC	System organ class
ULOQ	Upper limit of quantification
UN	Unstructured
VT	Vitality
VH:CD	Villous height to crypt depth ratio

WBC White blood cell

WHO DD World Health Organization Drug Dictionary

1 Introduction

This is a statistical analysis plan (SAP) for study CELIM-NRCD-001 which is based on the final study protocol CELIM-NRCD-001 Version 3 (dated 29AUG2016). This SAP describes the statistical analyses which will be presented in the clinical study report.

2 Study objectives

The study objectives are the following:

The **primary objective** of the study is:

- To assess the efficacy of AMG 714 in attenuating the effects of gluten exposure in adults with celiac disease.

The **primary efficacy endpoint** is:

- Attenuation of gluten-induced small intestinal mucosal morphological injury, measured morphometrically as villous height to crypt depth (VH:CD) ratio.

The primary endpoint of the study is the difference in the Baseline-to-Week-12 % change of VH:CD ratio between each of the two AMG 714 dose arms against the placebo arm.

The **secondary efficacy endpoints** of the study are:

- Attenuation of gluten-induced small intestinal mucosal inflammation measured as intraepithelial lymphocyte (IELs) density;
- Attenuation of gluten-induced small intestinal mucosal morphological injury using a grouped classification of Marsh score;
- Attenuation of gluten-induced serum antibodies (i.e. anti-tissue transglutaminase antibodies [anti-tTG] IgA, anti-deamidated gliadin peptide antibodies [anti-DGP] IgA and IgG);
- Attenuation of gluten-induced clinical symptoms (i.e. Bristol Stool Form Scale [BSFS], Gastrointestinal Symptom Rating Scale [GSRS] and celiac disease GSRS [CeD-GSRS]).

The secondary endpoints of Marsh score and total IEL counts will be evaluated by the change from baseline to Week 12 between the two AMG 714 dose arms and the placebo arm. Anti-tTG IgA, anti-DGP IgA and IgG will be evaluated by comparing the change from baseline in results obtained after every four weeks of two AMG 714 dose arms and placebo arm. BSFS, GSRS and CeD-GSRS will be evaluated by comparing the change from baseline in weekly scores of two AMG 714 dose arms and placebo arm.

The **secondary objective** of the study is:

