7.2 General statistical considerations

Descriptive statistics (e.g. mean, median, standard deviation (SD), minimum (MIN), maximum (MAX), and number of subjects with an observation (N) or missing observation (NMISS)) are used for summarizing continuous variables. Additional statistics will be provided for PK-related data, including the geometric mean, SD of log-transformed data, geometric CV%.

Frequencies and percentages are used for summarizing categorical variables.

All summary statistics will be presented by treatment arm and if repeated measures, then by visit/collection time point.

All listings will be created using ITT population. The PP and ITT flags for each subject will be included in all listings.

All tests will be two-sided, if not stated differently. P-values smaller than 0.05 will be considered statistically significant, if not stated otherwise. In addition to the inferential statistics, 95% confidence intervals will be constructed. For the primary endpoint for each of the dose levels a 95% confidence interval of the treatment difference will be constructed. Ninety-five percent (95%) confidence intervals will be constructed for the individual treatment point estimates.

Various covariates (baseline values, site and sex) will be included in the models to increase sensitivity of the tests and will be retained in the respective models regardless of their significance or lack thereof.

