7.2.1 Definition of derived variables

Geometric mean will be calculated as:

$$\text{mean}_{\text{geo}} = \sqrt[n]{x_1 x_2 \cdots x_n} = \exp\left\{\frac{1}{n} \sum_{i=1}^n \ln x_i\right\}.$$

Values that are missing or not available will be ignored in calculation of geometric mean.

CV%_{geo} will be calculated using the following formula:

$$\text{CV\%}_{\text{geo}} = 100\% \cdot \sqrt{\exp V_{\ln} - 1}.$$

Values that are missing or not available will be ignored in calculation of CV%_{geo}.

Absolute change from baseline for a given treatment needs to be calculated, the following formula will be used:

$$\text{Absolute change from baseline} = \text{Post-baseline value} - \text{Pre-dose value}.$$

For weekly scores, Week 0 score is considered to be the baseline value. If Week 0 score is not available, the first non-missing result within 2 weeks of treatment will be used as baseline. For daily scores (e.g. CeD PRO), Day 0 score is considered to be the baseline, in case Day 0 score is not available, the first non-missing result within 2 weeks of treatment will be used as baseline. Otherwise, the given subject will be considered non-evaluable for the specific test. In case pre-dose value doesn't exist (i.e. for biopsy endpoints), screening value will be used as baseline.

In the case where relative (%) change from baseline needs to be calculated, the following formula will be used:

$$\text{Relative (\%)} \text{ change from baseline} = (\text{Post-baseline value} - \text{Pre-dose value}) / (\text{Pre-dose value}) \cdot 100\%.$$

For weekly scores, Week 0 score is considered to be the baseline value. If Week 0 score is not available, the first non-missing result within 2 weeks of treatment will be used as baseline. For daily scores (e.g. CeD PRO), Day 0 score is considered to be the baseline, in case Day 0 score is not available, the first non-missing result within 2 weeks of treatment will be used as baseline. Otherwise, the given subject will be considered non-evaluable for the specific test. In case pre-dose value doesn't exist (i.e. for biopsy endpoints), screening value will be used as baseline.

Body mass index (BMI) is calculated using the formula:

$$\text{BMI (kg/m}^2\text{)} = \text{weight (kg)} / [\text{height (m)} * \text{height (m)}].$$

Body surface area (BSA) is calculated using Dubois' formula:

$$\text{BSA (m}^2\text{)} = 0.007184 * \text{height (cm)}^{0.725} * \text{weight (kg)}^{0.425}.$$

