The total weekly bowel movement counts will be analysed using generalized linear mixed models with subject as a random effect. The statistical model will include as fixed effects treatment group, sex, site, time (week) and time point-by-treatment group interaction. Poisson distribution with log-link will be used for modelling the counts. The following model will be fitted:

$$\log(Y_{ijklm}) = \mu + \tau_j + \varphi_k + \alpha_l + \gamma_m + \lambda_{lm} + \eta_i + \varepsilon_{ijklm},$$

where

Y_{ijklm} is the total bowel movement count for subject i ($i = 1, \dots, n_l$) from site j ($j = 1, 2, 3$), sex k ($k = 1, 2$) and treatment group l ($l = 1, 2, 3$) at visit m ($m = 3, 5, 7, 8$),

treatment group l ($l = 1, 2, 3$) at week m ($m = 0, 1, \dots, 16$),

μ is the overall mean on log-scale,

α_l is the fixed effect due to treatment l on log-scale,

φ_k is the fixed effect due to sex k on log-scale,

τ_j is the fixed effect due to site j on log-scale, γ_m is the fixed effect due to week m on log-scale,

λ_{lm} is the fixed interaction effect due to treatment l and week m on log-scale,

η_i is the random effect due to subject i ,

ε_{ijklm} is the random error for subject i from treatment group l for week m .

Due to the repeated structure of the data, the measurements within a subject will be correlated. Therefore, it is assumed that the overall covariance matrix of the response is block-diagonal. In order to determine the covariance structure that best fits the data, the same model with different covariance structures will be fitted. Initially, models will be fit assuming unstructured (UN) variance-covariance structure. Common within and between treatment variance components (compound symmetry (CS), first-order autoregressive (AR(1)) and Toeplitz covariance structures) will be further explored to increase sensitivity

of statistical tests. The best model will be chosen by comparing the Akaike Information Criterion (AIC) of the models with different covariance structures.

The following SAS code will be used to fit the above-specified model:

```

proc glimmix data=bsfs ic=q;
  class subjid trt sex site week(ref=FIRST);
  model bsfs = trt sex site week trt*week / solution dist=POISSON;
  random _residual_ / subject=subjid type=UN;
  estimate "150 mg AMG 714 vs Placebo" trt 1 0 -1 /alpha=0.05 cl ilink;
  estimate "300 mg AMG 714 vs Placebo" trt 0 1 -1 /alpha=0.05 cl ilink;
  estimate "Week 0: 150 mg AMG 714 vs Placebo" trt 1 0 -1

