    trt*week 0 0 0 0 0 0 0 0 0 0 0 0 0 0 0 0 0 0 1
    0 0 0 0 0 0 0 0 0 0 0 0 0 0 0 0 0 0 0
    0 0 0 0 0 0 0 0 0 0 0 0 0 0 0 0 0 0 -1
    /alpha=0.05 cl ilink;
  estimate "Week 0: 300 mg AMG 714 vs Placebo" trt 0 1 -1
    trt*week 0 0 0 0 0 0 0 0 0 0 0 0 0 0 0 0 0 0 0
    0 0 0 0 0 0 0 0 0 0 0 0 0 0 0 0 0 0 1
    0 0 0 0 0 0 0 0 0 0 0 0 0 0 0 0 0 0 -1
    /alpha=0.05 cl ilink;
  estimate "Week 1: 150 mg AMG 714 vs Placebo" trt 1 0 -1
    trt*week 1 0 0 0 0 0 0 0 0 0 0 0 0 0 0 0 0 0 0
    0 0 0 0 0 0 0 0 0 0 0 0 0 0 0 0 0 0 0
    -1 0 0 0 0 0 0 0 0 0 0 0 0 0 0 0 0 0 0
    /alpha=0.05 cl ilink;
  ...
  estimate "Week 16: 300 mg AMG 714 vs Placebo" trt 0 1 -1
    trt*week 0 0 0 0 0 0 0 0 0 0 0 0 0 0 0 0 0 1 0
    0 0 0 0 0 0 0 0 0 0 0 0 0 0 0 0 0 0 0
    0 0 0 0 0 0 0 0 0 0 0 0 0 0 0 0 0 0 -1 0
    /alpha=0.05 cl ilink;
  lsmeans trt /alpha=0.05 cl ilink;
  lsmeans trt*week /alpha=0.05 cl ilink;
  ods output CovParms=Cov_Par LSMeans=LS_est Estimates=Eff_est
    FitStatistics=Fit_Stat ParameterEstimates=Par_est
    Tests3=Type_3;
run;

```

Note that the value of `type` will be changed according to which covariance structure is being fitted.

The modelling results (parameter estimates, estimated ratio of the bowel movement rates in AMG 714 and placebo groups, estimated weekly ratios of the bowel movement rates in AMG 714 and placebo groups, marginal (i.e. least squares) means estimates and results of the check of assumptions, i.e. the over dispersion) will be tabulated and 95% confidence intervals added, where appropriate.

Weekly bowel movements and their BSFS types will be tabulated by treatment group and week and summarized by descriptive statistics, absolute numbers and percentages. Also, percentage of subjects with diarrhoea (at least 1 BSFS ≥ 6 for the week) and percentage of subjects with constipation (at least 3 days without bowel movement for the week) by week

and by treatment group will be presented. Individual and mean weekly bowel movement counts will also be presented graphically by time point and treatment group.

The daily bowel movement counts and their BSFS scores will only be listed.

PP populations will be used for the analysis.

Attenuation of gluten-induced clinical symptoms: Gastrointestinal Symptom Rating Scale (GSRS)

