α_j is the fixed effect due to treatment j ,

φ_l is the fixed effect due to sex l ,

τ_m is the fixed effect due to site m , β is the parameter estimate of the baseline total CeD PRO score,

γ is the parameter estimate of day,

λ_{jk} is the fixed interaction effect due to treatment j and day k ,

η_i is the random effect due to subject i ,

ε_{ijklm} is the random error for subject i from treatment group j , sex l and site m for day k .

Note that the proper functional form of the time (day) will be explored, e.g. square of day might be added.

The following SAS program will be used for carrying out the daily level analysis:

```

proc glimmix data=cedpro_d;
  class subjid trt site sex;
  model cedpro_d = cedpro_d_bl trt site sex day trt*day / solution;
  random _residual_ / subject=subjid type=AR(1);
  estimate "150 mg AMG 714 vs Placebo" trt 1 0 -1 /alpha=0.05 cl;
  estimate "300 mg AMG 714 vs Placebo" trt 0 1 -1 /alpha=0.05 cl;
  lsmeans trt /alpha=0.05 cl;
  ods output CovParms=Cov_Par LSMeans=LS_est Estimates=Eff_est
        FitStatistics=Fit_Stat ParameterEstimates=Par_est
        Tests3=Type_3;
run;

```

For the weekly level data, the following model will be fitted:

$$Y_{ijklm} = \mu + \alpha_j + \gamma_k + \lambda_{jk} + \beta \cdot baseline\ CeD\ PRO_{ijklm} + \eta_i + \varepsilon_{ijklm},$$

where

Y_{ijklm} is the total CeD PRO score for subject i ($i = 1, \dots, n_j$) from treatment group j ($j = 1, 2, 3$), sex l ($l = 1, 2$) and site m ($m = 1, 2, 3$) at week k ($k = 0, 1, \dots, 16$),
 μ is the overall mean,
 α_j is the fixed effect due to treatment j ,
 φ_l is the fixed effect due to sex l ,
 τ_m is the fixed effect due to site m ,
 γ_k is the fixed effect due to week k ,
 λ_{jk} is the fixed interaction effect due to treatment j and week k ,
 β is the parameter estimate of the baseline total CeD PRO score,
 η_i is the random effect due to subject i ,
 ε_{ijklm} is the random error for subject i from treatment group j , sex l and site m for week k .

The following SAS program will be used for carrying out the weekly level analysis:

```

proc glimmix data=cedpro_w;
  class subjid trt site sex week(ref=FIRST);
  model cedpro_w = cedpro_w_bl trt site sex week trt*week / solution;
  random _residual_ / subject=subjid type=AR(1);
  estimate "150 mg AMG 714 vs Placebo" trt 1 0 -1 /alpha=0.05 cl;
  estimate "300 mg AMG 714 vs Placebo" trt 0 1 -1 /alpha=0.05 cl;
  estimate "Week 0: 150 mg AMG 714 vs Placebo" trt 1 0 -1

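### The BSFS count model adjusts neither for the Week 0 baseline nor for recorded diary days, although the SAP defines BSFS by change from baseline and reports rates

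*SAP*

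**What the plan says.** Three general statements in the SAP bear on BSFS.

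- Section 2: "BSFS, GSRS and CeD-GSRS will be evaluated by comparing the change from baseline in weekly scores" across the two AMG 714 arms and placebo.
- Section 7.2.1: "For weekly scores, Week 0 score is considered to be the baseline value". If Week 0 is unavailable, the first non-missing result within two weeks of treatment replaces it.
- Section 7.2: "Various covariates (baseline values, site and sex) will be included in the models to increase sensitivity of the tests", and they are kept whether or not they are significant.

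The BSFS part of Section 7.6.2 sets out the model in prose: "The statistical model will include as fixed effects treatment group, sex, site, time (week) and time point-by-treatment group interaction". The formula has the same terms, with week running from 0 to 16. The code is "model bsfs = trt sex site week trt*week / solution dist=POISSON", and its contrasts include "Week 0: 150 mg AMG 714 vs Placebo". Among the results to be tabulated are the parameter estimates, the "estimated ratio of the bowel movement rates in AMG 714 and placebo groups" and the weekly ratios. Subjects are told to enter days without a bowel movement in the diary, so recorded days can be counted. Section 7.2.2 has no rule for incomplete diary weeks.

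**The concern.** The SAP declares a comparison of change from a Week 0 baseline, but the BSFS model has neither a change response nor a baseline covariate. Instead, Week 0 is one of 17 outcome weeks with an unconstrained arm effect. The antibody, GSRS, CeD-GSRS and CeD PRO repeated-measures models all carry a baseline term; for weekly CeD PRO the code is "model cedpro_w = cedpro_w_bl trt site sex week trt*week / solution".

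Stool frequency varies between people. With about 17 evaluable subjects per arm, ignoring an available measure of each subject's usual frequency can widen the confidence interval.

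Separately, the results are described as rates, but the response is the raw weekly total. A week with five recorded days is treated as if it had seven. If one arm completes the diary less fully, that difference passes into the treatment ratio.

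**Working it through.** **What the code produces.** The prose, formula and code agree that there is no baseline term and no offset. The freedom in Section 7.6.1 to modify SAS code therefore does not cover the omission. With `week(ref=FIRST)` and placebo as the last treatment level, each `trt*week` coefficient is the log ratio of change from Week 0 against placebo. Parameter estimates are on the list of tabulated results, so the quantity exists. It is not among the labelled treatment comparisons: those compare arms overall or within a week.

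**Inputs.** The SAP gives no precision figure for BSFS. The 17 per arm comes from Section 6. The primary-endpoint power there reproduces with a noncentral t, SD 36 and 48 df: 88.76% and 79.32% against the stated 88.8% and 79.3%. Everything else here is assumed: 10 stools per week, and a between-subject SD of the log rate of 0.4 or 0.15. The correlation ρ between a subject's true Week 0 and later log rates is 1 (stable) or 0.5.

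**Precision.** Let s = SD². On the log scale, Week 0 has variance Vb = s + 1/10, the mean of 15 outcome weeks has Vo = s + 1/150, and the covariance is c = ρs. The SE with the covariate, relative to the SE without it, is √(1 − c²/(Vo·Vb)).

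| SD | ρ | Overall ratio | Single week (Vo = s + 1/10) |
|---|---|---|---|
| 0.4 | 1 | √(1 − 0.0256/(0.1667 × 0.26)) = 0.64 | √(1 − (0.16/0.26)²) = 0.79 |
| 0.15 | 1 | 0.93 | 0.98 |
| 0.4 | 0.5 | 0.92 | 0.95 |
| 0.15 | 0.5 | 0.98 | 1.00 |

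Using 16 outcome weeks (Vo = s + 1/160) changes none of the overall figures at two decimals. A simulated repeated Poisson fit (two arms, 17 per arm, 1,000 runs per setting, without site or sex) gave 0.64 and 0.94 for ρ = 1, and 0.96 and 1.00 for ρ = 0.5. The range for the overall ratio is therefore about 0.64 to 1.00.

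**Change-from-Week-0 contrast as an alternative.** Its relative SE is √((Vo + Vb − 2c)/Vo): 0.80 (SD 0.4) and 1.91 (SD 0.15) for ρ = 1; 1.26 and 2.10 for ρ = 0.5. It can be much less precise than the unadjusted ratio.

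**Dilution.** The overall contrast averages over 17 weeks including Week 0. If a true ratio of 0.80 holds in Weeks 1 to 16 and there is no effect in Week 0, it reads 0.80^(16/17) = 0.81.

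**Diary completion (hypothetical; the SAP gives no data).** With no true effect and unrecorded days like recorded ones, 85% against 90% gives 0.85/0.90 = 0.94, 80% against 90% gives 0.80/0.90 = 0.89, and equal completion gives 1.00.

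**Costs of the remedy.**

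- *Covariate.* Six doses two weeks apart ending on Day 70 put the first dose on Day 70 − 5 × 14 = 0, so Week 0 may hold post-dose days. Suppose 25% of the log effect were already present in Week 0. With covariate slope b = s/(s + 0.1) = 0.615 or 0.184, a true 0.80 reads 0.80^(1 − 0.25b) = 0.83 or 0.81.
- *Offset.* At 10 stools per week under a Poisson count, P(zero day) = exp(−10/7) = 0.24. If all unrecorded days are zero days, and one arm records 60% of its zero days and the other all of them, the offset gives 1/(0.76 + 0.24 × 0.6) = 1.11, while raw totals give 1.00.

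**The case against.** The strongest reply is that nothing invalid is reported. In a randomised comparison, chance imbalance in usual stool frequency is sampling error, already reflected in the standard error and interval. A reader might infer that the headline ratios are biased by the missing baseline term. They are not, and the only distortion from keeping Week 0 is the small dilution of the overall ratio.

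A reader might also infer that change from baseline is not analysed at all. The documents do not support that, because the tabulated `trt*week` estimates contain it. What is missing is a labelled comparison.

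Nor is Section 7.2 a rule that every model must have a baseline covariate. It is a general statement, and the Marsh logistic model has none either. There, however, the response is itself improvement from baseline, whereas BSFS uses neither route. The conflict with Section 2 stands without Section 7.2.

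The remedy also has real costs: the covariate may absorb some early drug effect, and the offset can bias in its own way. The precision gain rests on assumptions and may be nil. All of this stands. It limits the weight of the point and is the reason for keeping the current model as a sensitivity analysis.

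Finally, a reader might infer from the Day 0 to Day 112 diary that Week 16 is too short for its tables. The SAP text does not map days to weeks, and the study schedule and table templates are appendices not shown, so that cannot be concluded.

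**Conclusion.** The point holds as a mismatch between the declared BSFS comparison and the model, with a possible loss of precision. It is not an error that invalidates the result. The textual omission is certain. Its size depends on assumed stool rates, between-subject spread and stability over time: the covariate could cut the SE of the overall ratio by about a third or leave it unchanged, and that of a single week by about a fifth or not at all.

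The missing exposure term matters only if diary completion differs between arms. Modest hypothetical differences would shift the ratio to 0.94 or 0.89. The sponsor should make the change, but it concerns one secondary endpoint and leaves the primary analysis untouched.

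**What to change.** In the BSFS part of Section 7.6.2, change prose, formula and code together:

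1. Add the log Week 0 daily rate, log((Week 0 count + 0.5)/recorded days), as a covariate. Remove Week 0, or the subject's fallback baseline week under Section 7.2.1, from the response. The ratios in the remaining weeks are then the labelled, baseline-adjusted comparison. Do not make the change-from-Week-0 contrast the main analysis, since it can raise the SE.
2. Add an offset equal to the log of the number of days with a diary entry, counting recorded zero days. Set weeks with no entry to missing.
3. Report the current unadjusted raw-total model as a sensitivity analysis.
4. State the two limits. Week 0 begins on the day of first dosing, so the covariate may absorb a little early drug effect; because active gluten starts only at Visit 2, Week 0 cannot contain a response to the challenge. The offset is biased if unrecorded days are mostly zero days.

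The cost is SAP wording, two derived variables (recorded days and baseline daily rate), a revised MODEL statement with matching contrasts, and one extra run. No new data are needed.

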7.7 Exploratory analysis

The exploratory endpoints of the study are:

- PGA;
- Biomarkers of disease activity;
- PK, and PK/PD correlations;
- CeD PRO;
- Assessment of the gluten-free diet (iVYLISA GIP stool test and urine gluten test).

7.7.1 Physician Global Assessment of Disease (PGA)

The PGA is designed to be used by the Investigator or qualified designee to assess the subjects' disease activity at the time points specified in the study schedule of events ([Appendix 1](#)). An attempt should be made to use the same assessor at each specified time point. Assessments should be made prior to study drug administration using all tools available to the assessor, including laboratory test values.

PGA will be tabulated by treatment group and visit. Change from baseline will also be presented by treatment group and visit. All PGA results will also be listed. Individual PGA results will additionally be plotted by visit and treatment group.

PP population will be used for summarizing PGA results.

7.7.2 Biomarkers of disease activity

Several biomarkers of disease activity will be analysed in serum and in biopsy tissue at the time points specified in [Appendix 1](#). The biomarkers of interest are:

- Serum IL-15 (pg/mL);
- Serum CRP (mg/L).

In addition, other exploratory biomarkers may be analysed, if deemed necessary.

The biomarkers of disease activity will be described by summary statistics, along with the change from baseline values and tabulated by treatment group and visit, if applicable. All individual results will be listed by visit. Individual and mean curves of biomarkers of disease activity will also be plotted by visit and treatment group, if applicable.

PP analysis population will be used for summarizing biomarker results.

